2.4.2 Prior or concomitant medications

The prior, concomitant and posttreatment medications will be presented in the randomized population for each treatment group (and overall for the summary of prior medications), using counts and percentages. No statistical test for the between-group difference will be performed.

Medications will be summarized by treatment group according to the WHO-DD dictionary, considering the first digit of the anatomic therapeutic chemical (ATC) class (anatomic category) and the first 3 digits of the ATC class (therapeutic category). A given medication may be classified in more than 1 ATC class. All ATC codes corresponding to a medication will be summarized, and a patient will be counted once in each ATC category (anatomic or therapeutic) linked to the medication. Therefore a patient may be counted several times for the same medication.

Prior medications will be presented by anatomic and therapeutic categories and sorted by decreasing frequency of ATC based on the overall incidence across treatment groups. In case of equal frequency regarding ATCs (anatomic or therapeutic categories), alphabetical order will be used.

Concomitant and posttreatment medications will be presented by anatomic and therapeutic categories and sorted by decreasing frequency of ATC based on the incidence in the Sotagliflozin 400 mg group. In case of equal frequency regarding ATCs (anatomic or therapeutic categories), alphabetical order will be used.

Antidiabetic medications will be presented separately by pharmacological class, chemical class and standardized medication name.

2.4.3 Extent of investigational medicinal product exposure and compliance

The extent of IMP exposure and compliance will be assessed and summarized by actual treatment within the safety population ([Section 2.3.2](#)).

2.4.3.1 Extent of investigational medicinal product exposure

The extent of IMP exposure will be assessed by the duration of IMP exposure

Duration of IMP exposure is defined as last dose date of double-blind IMP – first dose date of double-blind IMP + 1 day, regardless of unplanned intermittent discontinuations (see [Section 2.5.3](#) for calculation in case of missing or incomplete data).

Duration of IMP exposure will be summarized descriptively as a quantitative variable (number, mean, SD, median, minimum, and maximum) during the 26-week core treatment period and 52-week entire treatment period, respectively. In addition, duration of treatment exposure will also be summarized categorically by numbers and percentages for each of the following categories and cumulatively according to these categories:

- 1 to 28 days,
- 29 to 56 days,
- 57 to 84 days,
- 85 to 126 days,
- 127 to 182 days,
- 183 to 364 days,
- >364 days

Additionally, the cumulative duration of treatment exposure will be provided, defined as the sum of the duration of treatment exposure for all patients, and will be expressed in patient years.

Number and percentages of patients with dose interruption/reduction due to creatinine increase (identified as those who answered Yes to the question “If Actual Total Daily Dose is 0, Was the dose interruption due to creatinine increase per protocol?” in e-CRF “Exposure” page) will be summarized.

Number and percentages of patients by final dose at the end of the treatment will also be presented by each treatment group.

2.4.3.2 Compliance

A given administration will be considered noncompliant if the patient did not take the planned dose of treatment as required by the protocol. No imputation will be made for patients with missing or incomplete data.

Percentage of compliance for a patient will be defined as the number of days that the patient was compliant divided by the total number of days that the patient was planned to take during the treatment epoch defined in [Section 2.1.4](#) (ie, from the first to the last administration).

Above-planned dosing percentage for a patient will be defined as the number of days that the patient took a higher dose than planned divided by the total number of days that the patient was planned to take during the treatment epoch.

Under-planned dosing percentage for a patient will be defined as the number of days that the patient took a lower dose than planned divided by the total number of days that the patient was planned to take during the treatment epoch.

Treatment compliance, above-planned, and under-planned dosing percentages will be summarized descriptively as quantitative variables (number, mean, SD, median, minimum, and maximum). The percentage of patients whose compliance is <80% will be summarized. In addition, numbers and percentages of patients with at least 1 day above-planned dose will also be provided, as well as numbers and percentages of patients with (0, 20%], and >20% of days under-planned dose.

Cases of overdose (see study protocol for further details) will constitute AEs/SAEs and will be analyzed as such. More generally, dosing irregularities will be listed in [Section 2.2.1](#).

2.4.4 Analyses of efficacy endpoints

Efficacy analyses will be performed on the ITT population using the efficacy assessments collected during the study, including those obtained after IMP discontinuation or introduction of rescue therapy, unless otherwise specified.

Statistical testing will be performed for primary endpoint and secondary endpoints at Week 26 (with the exception of Week 12 for SBP). All efficacy endpoints after Week 26 will only be summarized by descriptive statistics without formal statistical testing.

Missing data for efficacy analyses is identified through steps described in [Section 2.5.4](#).

2.4.4.1 Analysis of primary efficacy endpoint(s)

The statistical tests will be two-sided tests at a nominal 5% significance level.

Primary analysis

The primary efficacy endpoint of change in HbA1c from baseline to Week 26 will be analyzed by an ANCOVA model using HbA1c values measured at baseline and Week 26 (observed or imputed). The missing data at endpoint will be imputed by multiple imputation (MI) methods in 2 parts as detailed below. To be concise, the following texts related to imputation are generalized to accommodate primary as well as continuous secondary efficacy endpoints.

1. Missing endpoint data for patients who prematurely discontinue the IMP before the Week 26 (or Week 12 for SBP) visit will be imputed using a model built separately in each treatment group and estimated from the patients in the same treatment group who prematurely discontinue the IMP before the Week 26 (or Week 12 for SBP) visit but have the measurement for the endpoint (retrieved dropouts). Considering that the number of patients in each treatment group who discontinue the IMP but have the measurement for the endpoint is expected to be small, a simple imputation model based on regression will be used with baseline measurement included as the predictor. Each treatment group will have their own imputation model.
2. Missing endpoint data for all patients who stay on the IMP until the Week 26 (or Week 12 for SBP) visit, including those in the sotagliflozin groups, will be imputed separately. The wash-out imputation method will be used, where missing endpoint data in the sotagliflozin groups, as well as in the placebo group are imputed from a model estimated from patients in the placebo group who stay on the IMP until the Week 26 (or Week 12 for SBP) visit and have the endpoint data available. The imputation model will include the randomization strata and the corresponding baseline value. Missing data will be imputed using the regression method.

An alternative (back-up) imputation method will be used if the number of patients who prematurely discontinue the IMP before the Week 26 (or Week 12 for SBP) visit but have the measurement for the endpoint is <5 in any treatment groups (ie, not sufficient retrieved dropouts to support the imputation method described above). This criterion will be assessed for each primary or continuous secondary efficacy endpoint separately.

In the back-up imputation method, missing post-baseline values will be imputed by control-based copy reference multiple imputation (MI) method under the missing not at random (MNAR) framework.

To compare sotagliflozin 400 mg and 200 mg, respectively, versus placebo

- For placebo patients, missing data will be imputed based on the placebo group data,
- For patients in the sotagliflozin 400 mg and 200 mg groups, missing data will be imputed as if the patients were on placebo throughout the study, where all patients' measurements including the on-treatment measurements will be considered as if the measurements were from the placebo group in the imputation model.

Using either imputation method, missing endpoint data will be imputed multiple times to generate multiple data sets with complete data (see sample code Part 1a or Part 2a of Appendix A). The change from baseline to Week 26 will be derived from observed and imputed HbA1c values at Week 26. Each of the complete datasets after the imputation will be analyzed by an Analysis of Covariance (ANCOVA) model with treatment groups (sotagliflozin 400 mg, sotagliflozin 200 mg, placebo), randomization stratum of HbA1c ($\leq 8.5\%$, $> 8.5\%$), randomization stratum of SBP (< 130 , ≥ 130 mmHg), and country as fixed factors, and baseline HbA1c value as a covariate (see sample code Part 4a of Appendix A). Results from each complete dataset will be combined using Rubin's formula, to provide the adjusted mean change in HbA1c from Baseline to Week 26 for each treatment group, as well as the between group difference (comparing sotagliflozin 400 mg, sotagliflozin 200 mg, respectively, versus placebo) and the 95% confidence interval (CI) for the between-group difference (see sample code Part 5 in Appendix A).

Sensitivity analyses

Tipping point analysis based on the same multiple imputation method as applied to the primary analysis will be performed to examine the robustness of the results from the primary analysis. Patients who were randomized to sotagliflozin groups and had no HbA1c data at Week 26 will be given a penalty. The penalty will be gradually increased to evaluate at which level the conclusion of the analyses in terms of statistical significance is changed. The tipping point is the penalty level, at which the magnitude of efficacy reduction in patients without HbA1c data at Week 26 creates a shift in the treatment effect of sotagliflozin 400 mg from being statistically significantly better than placebo to a non-statistically significant effect. LS mean difference between sotagliflozin 400 mg and placebo and its associated p-value will be provided for each penalty level. The steps to perform the tipping point analysis comparing sotagliflozin 400 mg versus placebo are as follows:

1. Missing data will be imputed using the same MI method as applied to the primary analysis (see sample code Part 3 in Appendix A),
2. The imputed HbA1c value at Week 26 in the sotagliflozin 400 mg group will be penalized by adding a penalty δ (eg, $\delta = 0.1\%$) in each complete dataset (see sample code Part 3 in Appendix A),
3. Change from Baseline at Week 26 in HbA1c will be analyzed using the same ANCOVA model as specified in the primary analysis in each complete dataset (see sample code Part 4a in Appendix A),
4. Results will be combined across complete datasets using Rubin's rule (see sample code Part 5 in Appendix A),
5. Steps 2 to 4 will be repeated with incremental penalty at δ (ie, δ , 2δ , 3δ ,.....) until the p-value for treatment effect of sotagliflozin 400 mg compared to placebo estimated in Step 4 is > 0.05 .

The above tipping point analysis will be replicated to examine the robustness of the treatment effect of sotagliflozin 200 mg (ie, adding penalty to the sotagliflozin 200 mg group instead of sotagliflozin 400 mg group in Step 2).

The tipping point analysis will be performed on the ITT population. The tipping point analysis will be performed only if the corresponding primary or secondary variables (change from Baseline to Week 26 in HbA1c) is statistically significant at $\alpha = 0.05$ (2-sided).

If the retrieved dropout imputation is applied to the primary analysis, the analysis based on the control-based imputation (ie, the backup imputation method) will be presented as a sensitivity analysis.

Assessment of treatment effect by subgroup

Descriptive analyses will be performed on the primary endpoint to summarize the treatment effects across subgroups defined by the following Baseline or Screening factors:

- Race (White, Black or African American, Asian, Other) (any race groups with fewer than 5 patients may be combined with “Other” category as appropriate),
- Ethnicity (Hispanic, Not Hispanic),
- Age group (<50, ≥ 50 to <65, ≥ 65 years) (any category with fewer than 5 patients may be combined with another category as appropriate),
- Gender (Male, Female),
- Baseline BMI level (<30, ≥ 30 kg/m²),
- Baseline HbA1c ($\leq 8.5\%$, $> 8.5\%$),
- Baseline mean SBP (<130 mmHg, ≥ 130 mmHg),
- Duration of diabetes (<10, ≥ 10 years),
- Prior antidiabetic medication (insulin, non-insulin),
- Country.

The treatment effect (sotagliflozin 400 mg versus placebo) across the subgroups defined for each of these factors will be estimated for the change from Baseline to Week 26 in HbA1c in the ITT population, and using the same MI method as applied to the primary analysis as applied to the analysis for the primary efficacy endpoint. The ANCOVA model will include treatment groups (sotagliflozin 400 mg, sotagliflozin 200 mg, placebo), randomization stratum of HbA1c ($\leq 8.5\%$, $> 8.5\%$), randomization stratum of SBP (<130, ≥ 130 mmHg), subgroup factor, treatment-by-subgroup factor, and country as fixed factors and using baseline HbA1c value as a covariate. The adjusted estimates of treatment mean differences (sotagliflozin 400 mg versus placebo) with standard error (SE) and 95% CIs will be provided as appropriate across the subgroups (see sample code Part 4a in [Appendix A](#)). A graphical presentation of the results (ie, forest plot) will also be provided.

Similarly, the treatment effect across the subgroups will be estimated for the comparison of sotagliflozin 200 mg versus placebo as a sensitivity analysis.

In the case that the subgroup factor is identical or similar to a randomization strata factor (eg, baseline HbA1c or baseline mean SBP category), only the subgroup factor (as a single factor or an interaction term) will be included in the model in order to avoid the issue of collinearity in the analysis. The corresponding strata factor will not be included in the model.

Summary statistics at scheduled visits

Summary statistics (for screening value, baseline value, observed post-baseline value and its changes from baseline) at scheduled visits will be provided for each treatment group. The summary will include the number of observations, mean, SD, SE, minimum, median, and maximum. Graphical presentations will also be used to examine trends over time using mean values (\pm SE) and mean changes from baseline (\pm SE) at each of the scheduled visits.

Similar presentations will be provided excluding measurements after rescue therapy during the entire 52-week double-blind treatment period.

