### **10.3.3 List of criteria for permanent treatment discontinuation**

The patients may withdraw from treatment with the IMP if they decide to do so, at any time and irrespective of the reason, or this may be the Investigator's decision. Patients should discuss stopping study medication with the site before doing so in order that questions can be addressed, glycemic therapy adjusted, and a follow-up assessment arranged. All efforts should be made to document the reasons for treatment discontinuation and this should be documented in the e-CRF.

The following reasons can lead to permanent discontinuation:

- At the patient's own request (ie, withdrawal of consent for treatment)
- If, in the Investigator's opinion, continuation with the administration of the study treatment would be detrimental to the patient's well-being
- Inter-current condition that requires permanent discontinuation of the study treatment as long as the abnormality persists and if the casual relationship of the concerned event and the IMP is possible (according to the Investigator's best medical judgment)
- Deterioration of renal function (defined as increase in serum creatinine >50% from baseline) that is not recovered after a temporary IMP discontinuation for 2 weeks
- Patient requires renal replacement therapy (transplant or dialysis)
- Pregnancy (in female patients)
- Specific request of the Sponsor.

Any abnormal laboratory value will be rechecked immediately to confirm the result before a decision is made to permanently discontinue IMP for the concerned patient.

For patients who prematurely discontinue the IMP, the assessments planned at EOT visit ([Section 10.1.3.2](#)) will be performed at the premature EOT Visit scheduled preferably prior to treatment discontinuation or as soon as possible after the time of discontinuation (at the latest at the next scheduled on-site visit). In the case of premature IMP discontinuation, PK samples

should not be drawn at the premature EOT visit, neither at all subsequent visits. The reason for IMP discontinuation will be clearly specified. This Premature EOT assessment may occur at a regularly scheduled visit or at an unscheduled visit.

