#### **10.3.4 Handling of patients after permanent treatment discontinuation**

Every effort should be made to maintain patients in the study. Patients should be followed up according to the study procedures as specified in this protocol up to the scheduled date of study completion, or up to recovery or stabilization of any AE to be followed up as specified in this protocol, whichever comes later.

If a patient prematurely discontinues study treatment, a premature EOT visit (see [Section 10.1.3.2](#)) should be scheduled prior to treatment discontinuation, if possible. If not possible, the Premature EOT should be scheduled as soon as possible after treatment discontinuation. In the case of early discontinuation, no sample for measuring plasma concentration should be taken at the premature EOT visit, or at any subsequent visit. For patients who discontinue treatment but remain in the study, the remaining study visits should occur as scheduled where possible. The IRT should be notified of EOT.

All cases of permanent treatment discontinuation should be recorded by the Investigator in the appropriate pages of the e-CRF.

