2.5.4 Windows for time points

The following steps will decide how the scheduled and/or unscheduled visits will be used in the analyses on efficacy variables and the by-visit summaries for safety variables (clinical laboratory data in Section 2.1.4.4 and vital signs in Section 2.1.4.5).

Step 1 A scheduled measurement will be used if it is available; otherwise, an unscheduled measurement (including the end of treatment/study visit for those prematurely discontinued) will be used if it happens to be on the same date as the date of the scheduled visit.

Step 2 After Step 1, if there are still no measurement for a given parameter at a scheduled visit, the analysis window below (Table 4) will be applied to re-allocate a post-baseline unscheduled measurement to a scheduled measurement.

Table 4 - Analyses window definition

Scheduled visit post baseline	Targeted study day	Analysis window in study days
Week 1 (Visit 4)	7	2 to 10
Week 2 (Visit 5)	14	11 to 17
Week 3 (Visit 6)	21	18 to 24
Week 4 (Visit 7)	28	25 to 41
Week 8 (Visit 8)	56	42 to 69
Week 12 (Visit 9)	84	70 to 104
Week 18 (Visit 10)	126	105 to 153
Week 26 (Visit 11)	182	154 to 227
Week 39 (Visit 12)	273	228 to 318
Week 52 (Visit 13)	364	≥319

Study days are calculated from the day of first administration of double-blind IMP; the day of first administration of IMP (or the day of randomization if not exposed) is Day 1.

After applying the above time windows, if multiple assessments are associated to the same time point, the closest from the targeted study day will be used. In case of equality, the last measurement will be used. Re-allocated scheduled visits (ie, visit numbers) should be sequential if ordered by the date of measurement.

After Step 2, if there are still no measurement for a given parameter at a scheduled visit, data is considered missing for efficacy analyses, where multiple imputation would be applied as appropriately as described in [Section 2.4.4](#).

Reference day

The reference day for the calculation of extent of exposure, time to onset, and relative days will be the day of the first administration of double-blind IMP or the day of randomization if not exposed to double-blind IMP, denoted as Day 1.

Baseline definition for efficacy/safety data

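### The SAP's retrieved-dropout definition lets an end-of-treatment value taken on drug serve as an off-drug donor and count towards the five-donor minimum that selects the primary imputation method

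*SAP*

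**What the plan says.** **Donors.** SAP 2.4.4.1 (part 1 of the primary imputation) builds a regression in each arm from patients "who prematurely discontinue the IMP before the Week 26 (or Week 12 for SBP) visit but have the measurement for the endpoint (retrieved dropouts"). SAP 1.6 repeats this definition. In Appendix A Part 1 the step selects on the discontinuation flag alone. That flag is missing from the variable list at the head of the appendix, and no date condition is attached to the endpoint value.

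**Switch.** If any arm has fewer than 5 such patients for an endpoint, SAP 2.4.4.1 replaces the method with control-based copy-reference imputation.

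**Which value counts as Week 26.** SAP 2.5.4 gives precedence to a scheduled measurement. Failing that, it turns to "an unscheduled measurement (including the end of treatment/study visit for those prematurely discontinued"), first if taken on the date of the scheduled visit. In Step 2 the Table 4 window "will be applied to re-allocate a post-baseline unscheduled measurement to a scheduled measurement". The Week 26 window is Days 154-227 (target 182) and the Week 12 window is Days 70-104 (target 84). Only then does a gap count as missing: "After Step 2, if there are still no measurement for a given parameter at a scheduled visit, data is considered missing for efficacy analyses".

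**When the EOT visit is held.** Protocol 10.3.3 describes a "premature EOT Visit scheduled preferably prior to treatment discontinuation or as soon as possible after the time of discontinuation", at the latest by the next scheduled on-site visit. Protocol 10.3.4 says the visit "should be scheduled prior to treatment discontinuation, if possible". It follows the Visit 13 procedures, which include HbA1c and blood pressure.

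**The concern.** A retrieved dropout is useful as a donor because its value shows the endpoint after treatment has ended. The rules above admit a value that shows the opposite. Suppose a patient has the EOT visit on Day 156, takes the last dose that day and does not return. The patient stopped before Week 26 and has a re-allocated Week 26 HbA1c, so both donor conditions are met with an on-drug measurement. That value then informs imputation for patients who may have been off drug for months.

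Two things are at stake. In the sotagliflozin arms such a donor carries treatment effect into patients who stopped, while in the placebo arm it carries none, so the direction favours the drug. The same record also counts towards the minimum of 5, so on-drug values can help to decide which imputation method is primary.

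**Working it through.** **Plan's own figure.** With difference 0.5, SD 1.2 and two-sided 0.05, power at 92 per group is 0.807 (normal approximation) or 0.803 (noncentral t; 0.798 at 91). The stated 92 per group reproduces and is used as the arm size below. The point does not affect it.

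**Exposed days.** Week 26: 182 − 154 = 28 of the 181 days before target, 28/181 = 15.5%. Week 12: 84 − 70 = 14 of 83 days, 14/83 = 16.9%.

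**Assumptions not in the documents.** A proportion d of each arm stops before Week 26, uniformly over Days 1-181 (d = 10%, 20%, 30%). A proportion r of those who stop return at Week 26 (r = 30%, 50%, 70%). Of those who do not return, 80% had the EOT visit on or before the last dose. The full 0.5-point effect is present on drug and none of it off drug.

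**Formulas, per arm.**
- Late stops: 92 × d × 28/181 = 1.4, 2.8 and 4.3 for d = 10%, 20%, 30%. This is a ceiling, since returners are unaffected.
- On-drug donors: E = 92 × d × (28/181) × (1 − r) × 0.8.
- True donors: T = 92 × d × r.
- Shift through imputation: 0.5 × E/(T + E) × (92d − T − E)/92.
- Shift from the re-allocated patients' own values: 0.5 × E/92.

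| d, r | T | E | E/(T+E) | imputation shift | own-value shift |
|---|---|---|---|---|---|
| 10%, 70% | 6.4 | 0.34 | 5% | 0.001 | 0.002 |
| 20%, 50% | 9.2 | 1.1 | 11% | 0.005 | 0.006 |
| 20%, 30% | 5.5 | 1.6 | 22% | 0.014 | 0.009 |
| 30%, 30% | 8.3 | 2.4 | 22% | 0.021 | 0.013 |

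Across the nine combinations E runs from 0.3 to 2.4 and the total shift from about 0.003 to 0.034 points. The standard error of the difference is 1.2 × √(2/92) = 0.177.

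**The switch.** The chance that on-drug values lift a given arm from below 5 to at least 5 donors is 0% to 19%, highest at d = 20%, r = 30%. The method depends on all three arms. In that worst case true donors are Binomial(92, 0.060) and all donors Binomial(92, 0.0773), so the chance of at least 5 is 0.653 and 0.848. With equal, independent arms the chance that the method changes is 0.848³ − 0.653³ = 0.610 − 0.278 = 0.33. By the same calculation it is 0.17 at d = 30%, r = 30%, and below 0.10 in the other seven combinations.

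**Week 12 SBP.** With d = 10-20% by Week 26, stops before Week 12 number 92 × d × 83/181 = 4.2 to 8.4 per arm. Those on Days 70-83 number 92 × d × 14/181 = 0.7 to 1.4.

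**The case against.** **The patient may not be classed as discontinued.** Step 2 re-allocates visit numbers, so the EOT visit could be read as having become Visit 11. A patient dosed up to that day would then have stayed on IMP until Week 26, and would not be a retrieved dropout. This ambiguity is real. The SAP leans the other way: 2.5.4 uses Day 182 when the Visit 11 date is missing, expressly to define end-of-treatment status at Week 26, and its censoring table keeps the Week 26 visit date apart from re-allocated Week 26 values. Even on the kinder view, two programmers could reach different donor counts, which supports a written definition.

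**Several conditions must coincide.** This stands. Discontinued patients are asked to keep attending, particularly at Week 26, and a scheduled value takes precedence. A pre-stop EOT visit is a preference. In the creatinine pathway IMP has already been interrupted for 2 weeks, so an EOT visit at permanent discontinuation is off drug.

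**Planned sensitivity analyses cover it.** Partly. The tipping-point analysis penalises imputed HbA1c values, and the control-based analysis is presented whenever retrieved-dropout imputation is primary. A change of method is therefore not hidden. But the penalty omits patients with a Week 26 value, the control-based analysis keeps their on-drug value as observed, and the analysis in SAP 1.6 uses the same donor definition.

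**Stronger readings a reader might infer.**
- *One such donor among five moves imputed values by 0.10 points (0.5/5).* That is an upper bound. It needs complete loss of effect off drug, whereas protocol 9.5 says HbA1c reflects the past 2 to 3 months.
- *The problem is worse for Week 12 SBP.* The documents do not say how fast SBP reverses. With only about 4 to 8 stops per arm before Week 12, and 5 with values needed in every arm, the back-up method would often apply and the donor problem would not arise.
- *The on-drug value should be set to missing.* SAP 2.1.3 and 2.4.4 use all collected efficacy measurements. Discarding an observed in-window value conflicts with that.

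**Conclusion.** The point holds in a limited form. The donor definition, the re-allocation rule and the preferred timing of the EOT visit together admit on-drug values as off-drug donors, and no text excludes them. It probably touches no more than 1 to 3 patients per arm. The HbA1c difference moves by a few hundredths of a point at most, in favour of the drug: at the extreme 0.034/0.177, about a fifth of a standard error. A shift of that size is unlikely to change a conclusion, and the documents do not support a claim of material bias in the primary estimate.

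The possible change of primary imputation method matters more, mainly where true retrieved dropouts average about 3 to 8 per arm. All sizes rest on assumed discontinuation, return and visit-timing rates, and on full loss of effect off drug, which overstates the HbA1c shift.

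**What to change.** 1. In SAP 2.4.4.1, SAP 1.6 and Appendix A Part 1, require a donor's endpoint value to be dated after that patient's last dose of IMP.
2. Apply the fewer-than-5 check to donors so defined, endpoint by endpoint.
3. Define the discontinuation flag by the last-dose date relative to the actual Visit 11 date (Visit 9 for SBP), or to Day 182 (Day 84) if that visit was not held. Day 182 is already the SAP's fallback; Day 84 is the matching Table 4 target.
4. Keep a re-allocated value as the patient's own observed endpoint. In the code these records should pass unchanged into every completed dataset, as already happens for sotagliflozin patients who stayed on IMP with observed values. This removes the donor channel (0.001 to 0.021 points above) and leaves the own-value part (0.002 to 0.013).
5. SAP 1.6 states that the first-step analysis was conducted and reported for top-line results. So report the number of donors per arm whose value is dated on or before the last dose, state whether excluding them changes the fewer-than-5 outcome, and present the corrected analysis alongside the original under SAP 1.6.

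The cost is a few lines of SAP text and one date condition in the code. The downside is slightly fewer donors, so the back-up method would apply a little more often. The condition does not remove HbA1c carry-over in values taken soon after the last dose.
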